6.4.4 Treatment compliance

At all times, when dispensing study drug, research center personnel will review the instructions, printed on the packaging, with subjects. Subjects will be asked to maintain a diary to record the drug administration.

6.5 Radiation Therapy

6.5.1 Selection of a target lesion

All patients should have at least 2 measurable sites of disease (one target lesion and one or more lesions for response assessment). The target lesion for radiation should measure a minimum of 1 cm and a maximum of 8 cm in greatest diameter. The lesion least likely to result in normal tissue toxicity should generally be selected for treatment at investigator discretion. Suitable targets include lymph nodes and extranodal tumor deposits. CNS disease is NOT a suitable target and patients with CNS involvement are not eligible for enrollment.

6.5.2 Treatment planning/target volumes

GTV: Will include visible target lesion as identified by diagnostic and/or treatment planning CT or PET and clinical exam

PTV: An additional margin of 5-10 mm will be added to account for setup error at treating physician discretion.

If clinical setup is used, a 1.5 cm block margin on clinically apparent disease should be applied

6.5.3 Dose specifications

All patients will receive a dose of 20 Gy delivered in 5 daily fractions of 4 Gy each. At least 95% of the GTV should receive the full prescription dose of 20 Gy. Coverage may be estimated in the case of clinical set-up.

6.5.4 Technical parameters

Radiation will be delivered with megavoltage equipment at photon energies ≥ 6 MV or with electron fields ≥ 4 MeV. Cobalt-60 and proton beams are not permitted. Any beam arrangement that allows for optimal coverage of the target lesion and minimizes dose to surrounding structures is permitted.

6.5.5 Immobilization and simulation

Patients will be positioned reproducibly with a customized thermoplastic immobilization cast or a molded foam cradle as needed or stabilization. CT simulation is encouraged, but clinical set-up is permitted for superficial lesions that can be easily demarcated without CT simulation.

6.5.6 Normal critical structures and dose constraints

Normal critical structures located within 5 cm of the PTV should be delineated and dose should be tracked, including but not limited to: Spinal cord, lungs (right and left), heart, esophagus, liver, small bowel, large bowel, bladder, rectum, brain, orbits (right and left), brainstem. As the prescription dose is such that normal tissue tolerance is generally not expected

6.5.7 Treatment Verification and Image Guidance

At the start of treatment, electronic portal imaging should be used to verify treatment fields. More frequent imaging is permitted but not required.

6.5.8 Radiation Adverse Events

Adverse Events will be categorized and graded based on the Common Toxicity Criteria for adverse events Version 4.0 (CTCAE version 4.0).

Radiotherapy should be discontinued for Grade 4 in-field toxicity

6.6 Concomitant therapy

All medications (prescription and non-prescription), treatments, and therapies taken from the first day of study drug through the end of the study, must be recorded on the source documents.

6.6.1 Recommended concomitant therapy

The use of filgrastim (G-CSF) for subjects in this study is permitted when used to treat neutropenia. Subjects should receive full supportive care, including transfusions of blood and blood products, antibiotics, and antiemetics when appropriate.

Use of steroids is allowed in emergencies including the management of infusion reactions to rituximab.

6.6.1.2 Anticoagulation Consideration

Lenalidomide likely increases the risk of thrombotic events in patients who are at high risk or with a history a thrombosis, in particular when combined with other drugs known to cause thrombosis. Based on data with thalidomide it has been hypothesized that when lenalidomide is combined with other agents such as steroids (e.g. dexamethasone, prednisone), anthracyclines (Doxil, adriamycin) and erythropoeitin the risk of thrombosis may be increased.

The use of aspirin (81 or 325 mg) or some other form of prophylaxis as deemed appropriate is required. Low molecular weight heparin may be utilized in patients that are intolerant to ASA. Coumadin should be used with caution and close monitoring of INR at the discretion of the PI. Hold anticoagulation for platelet count < 50,000 mm³.

6.6.1.3 Prohibited concomitant therapy

Concomitant use of sargramostim (GM-CSF), other anti-cancer therapies, including radiation, thalidomide, or other investigational agents is not permitted while subjects are receiving study drug during the treatment phase of the study. Concomitant use of other anti-lymphoma therapy, including steroids (except for the treatment of hypersensitivity reactions), while the subject is on study drug is prohibited.

6.7 Discontinuation of Study Treatment

Treatment will continue until evidence of disease progression or the occurrence of any of the following events.

Treatment with study drug is to be discontinued when any of the following occurs:

- Lack of the rapeutic effect/progressive disease as defined in section 8.0
- Adverse event(s) that, in the judgment of the Investigator, may cause severe or permanent harm or which rule out continuation of study drug.
- Major violation of the study protocol.
- Withdrawal of consent
- Lost to follow up
- Death
- Suspected pregnancy
- Treatment may also be discontinued after a total of twelve cycles of treatment if a patient achieves and maintains a complete response. This will be decided by the treating physician.

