Radiotherapy is frequently employed as a treatment strategy for indolent lymphoma, either as curative intent therapy for early stage (I/II) disease, or a palliation for symptomatic advanced disease. Low grade lymphoma is typically exquisitely sensitive to radiotherapy, with palliative responses identified in high percentage of patients treated with doses as low as 4 Gy over 2 fractions [8-9]. Local radiotherapy is consistently well-tolerated in this patient population with low rates of grade 3+ toxicity [8].

Emerging clinical data suggest local radiotherapy may exhibit potent systemic immunomodulatory effects when delivered in combination with systemic immunotherapy agents, and in select cases may generate a systemic response (in non-radiotherapy target lesions) in patients previously refractory to immunotherapy alone. Case reports/series in melanoma patients describe impressive systemic effects following local radiotherapy in patients previously refractory to the immune checkpoint (CTLA-4) inhibitor ipilimumab [10-11]. Such effects are not well-studied yet for lenalidomide, However, lenalidomide is a potent immunomodulatory agent that exhibits both tumoricidal and anti-proliferative effects. There is evidence that lenalidomide may exert its antitumor effects by reversing the defective ability of T cells and NK cells to form synapses with malignant B cells thereby enhancing immune-mediated cytotoxicity. We hypothesize that in the presence of tumor antigens that are released as a result of local tumor irradiation, lenalidomide will mediate a response at distant sites in patients that were previously refractory to lenalidomide.

We propose employing this strategy in patients who progress on the combination of lenalidomide and rituximab. Patients will continue lenalidomide while undergoing local radiotherapy to a single site of disease, with re-staging every 2 months to assess for local and distant response. Lenalidomide will then be continued until disease progression.

- 1. Corral LF, Kaplan G et al. Differential cytokine modulation and T cell activation by two distinct classes of thalidomide analogues that are potent inhibitors of TNF-alpha. J Immunol. 1993;163:380-386.

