Response rate (overall and complete) in non-target lesions following local radiation with concurrent lenalidomide in patients previously refractory to the combination of lenalidomide and rituximab.

STUDY DESIGN:

The study will be a multi-institution, phase II clinical trial in patients with previously untreated indolent Non-Hodgkin's lymphoma. Patients will receive lenalidomide 20 mg daily, on days 1-21 of a 28 day cycle. Rituximab 375 mg/m2 will be administered weekly for 4 doses starting day 15 of cycle 1, to be repeated if patient does not achieve a complete response after cycle 4, on days 1, 8, 15 and 22 of cycle 5. Therapy with lenalidomide may be discontinued after twelve cycles if the patient achieves a complete response.

Patients progressing on lenalidomide and rituximab will be offered treatment in a radiotherapy cohort. Patients will continue lenalidomide at the current dose, on days 1-21 of a 28 day cycle. Local fractionated radiotherapy will be delivered to a single site of disease days 1-5 of a 28 day

cycle to 20 Gy in 4 Gy fractions. Re-staging will be performed every 2 months, and lenalidomide will be continued until disease progression or intolerance.

STUDY ENDPOINTS:

Primary:

Complete response (CR), near complete response (CRu), or partial response (PR), stable disease (SD) of 4 months.

Secondary:

Time to disease progression, tolerability, duration of response, overall survival, and tumor control rate from the start of treatment.

Measurement of immune profile

STUDY DURATION:	TOTAL SAMPLE SIZE:
Patients will be enrolled over 2yrs.	Approximately 30 patients
	Of the 30 total patients 10 progressing patients will be offered optional treatment on the radiotherapy arm
DOSING REGIMEN(S):	STUDY DRUG SUPPLIES:
Lenalidomide will be initiated at 20 mg daily, days 1-21 of a 28 day cycle, to be continued until disease progression, unacceptable toxicity or after twelve cycles if the patient has achieved a complete response. Rituximab 375 mg/m2/wk x 4 weeks, to begin Day 15 of cycle 1. After 4 cycles of therapy if patient	Celgene Corporation will supply lenalidomide as 5 mg capsules.
does not achieve CR, the patient will receive a second course of Rituximab.	
Blood samples for companion study to assess immune profiles will be obtained within 1 week	
prior to starting treatment & then on days 15, 30,	
60 and 120, and then at the end of treatment or	

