when treatment is discontinued for any reason. Additional blood draws for immunologic profiling	
at day 15, 30 after starting radiation therapy and at	
the time of progression for patients taking part in	
the additional radiation therapy cohort. If the patient progresses within 8 weeks, the blood draw	

at progression will not be done.

After progression: Lenalidomide will be continued at the current dose, days 1-21 of a 28 day cycle. Radiotherapy will be delivered in a single course of 20 Gy in 5 daily fractions of 4 Gy each, day 1-5 of a 28 day cycle. Lenalidomide will be continued until disease progression, unacceptable toxicity or after twelve cycles if the patient has achieved a complete response.

Confidential Page 14 of 80

UCDCC#224 Celgene # RV-NHL-PI-0488 Version Date: 09/10/18

2 Schedule of Study Assessments

Procedure	Screening ≤ 28days from Baseline (First		Cyc	le 1		Cyc	cle 2	All other cycles	At Progression ¹⁸	Discontinuation From Study Drug	Follow- Up Phase	Post- Progression Radiation ¹⁹
	day study drug administration)	Day 1	Day 8	Day 15	Day 22	Day 1	Day 8	Day 1			Every 3 months	
Record prior medications, treatments	X		100									
Record prior anti-cancer therapies	X											
Physical examination, vital signs, weight	X					X		X^{13}	X	X		X
ECOG performance status	X					X		X^{13}	X	X		X
CT/PET ¹⁴ or CT of the chest & abdomen / pelvis (as clinically indicated)	X^1	Repe	at every	8 weei	ks while	e recein	ving tre	atment ⁷		X		X^{20}
Bone scan ² (as clinically indicated)	X^2		1/5									
Bone marrow Biopsy and aspirate	X ⁸		.30							Ĭ		
Colonoscopy and Bx (as clinically indicated)	X ⁸		100									
CT or MRI of the brain (as clinically indicated)	X^3		134									
ECG	X		196					0,000			de de	
Hematology (Blood counts)	X	7/2	X	X	X	X		X^{13}	X	X		X
Serum chemistry and tumor lysis labs ⁴ (Note: TSH measured as clinically indicated)	X	X/X	X/X	X/X	X/X	X		X ^{4, 13}	X	X^4		X
Immune profile ¹⁰	X	X/X	33	X/X				X^{10}	X	X		X^{22}
Peripheral blood PCR for t(14,18) ¹⁶ (as clinically indicated)	X		si.		2			X ¹⁶	X		9	X
Pregnancy test 5	X^6		X	X	X	X^6		$X^{6,13}$		X^6		
HIV test ¹⁷	X									Î		
Hepatitis B tests	X	70	×									
Register patient into Revlimid	X	-	rd.		2					10		

Procedure	Screening ≤ 28days from Baseline (First	Cycle 1				Cycle 2		All other cycles	At Progression ¹⁸	Discontinuation From Study Drug	Follow- Up Phase	Post- Progression Radiation ¹⁹

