5.3 Overall design

The study is a phase II clinical trial with all patients to be accrued at UCD Cancer Center and other participating centers. All patients who are eligible will receive both lenalidomide and rituximab.

- Lenalidomide will be started at 20 mg daily, days 1-21 of a 28 day cycle.
- A total of 30 patients will be evaluated in this study.
- Rituximab 375 mg/m2/wk x 4 weeks, to begin on day 15 of cycle 1. After 4 cycles of therapy if a patient has not achieved a CR, the patient will be given a second course of Rituximab, on days 1, 8, 15 and 22 of cycle 5.

Patients who progress through this combination will be offered optional participation in a radiotherapy cohort. Up to 10 patients who consent will continue lenalidomide and receive local radiotherapy to a single target lesion.

- Lenalidomide will be continued at the patient's most recent dose daily, days 1 21 of a 28 day cycle.
- Radiotherapy will be delivered to a single involved site to a dose of 20 Gy over 5 daily fractions of 4 Gy each, day 1-5, using electron or photon beams with a conventional linear accelerator.

Investigational Drugs

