6.1 Treatment Schedule

Lenalidomide capsules will be taken orally in the morning each day on days 1 - 21, followed by 7 days of no therapy of each 28-day cycle. Rituximab will be given by intravenous infusion weekly for 4 weeks beginning on day 15 of treatment start, thus on days 15, 22 of cycle 1 and days 1 and 8 of cycle 2.

Following cycle one, therapy with lenalidomide will continue in 28-day cycles, until there is disease progression, unacceptable toxicity or the patient chooses to withdraw from therapy. Lenalidomide may be discontinued after twelve cycles if complete response demonstrated, per physician and patient discretion. Additional course of rituximab will be administered if CR not attained after cycle 4, to be administered during cycle 5 on days 1, 8, 15 and 22. The patient must see the study physician before the next cycle may begin. There will be a +/-3 day window for study visits and procedures after completion of cycle one.

Dosing regimen

The planned maximum dose of lenalidomide for investigation is 20 mg daily, days 1-21 of a 28 day cycle. Dosing will be in the morning at approximately the same time each day. Lenalidomide may be taken orally either with a full or an empty stomach.

Due to the uncertain amount of re-absorption of lenalidomide, there will be no re-dose for lenalidomide if the patient vomits the pills.

Lenalidomide capsules should be swallowed whole, and should not be broken, chewed or opened.

If a dose of lenalidomide is missed, it should be taken as soon as possible on the same day. If it is missed for the entire day, it should not be made up.

Patients who take more than the prescribed dose of lenalidomide should be instructed to seek emergency medical care if needed and contact study staff immediately.

Prophylactic anti-coagulation is required during lenalidomide treatment. See Section 6.5.1.2.

Rituximab 375 mg/m2/week will be administered by IV infusion starting on day 15 from start of treatment and will continue weekly for 4 weeks (a total of four doses). The course of rituximab will be repeated if CR not attained after cycle 4. It will be administered at 375 mg/m2 weekly during cycle 5 on days 1, 8, 15 and 22.

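### Sections 6.1 and 6.7 make no exception for the radiotherapy cohort, and section 8 does not reset the progression reference at cohort entry, so unchanged disease can count as new progression

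*Combined protocol and SAP*

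**What the plan says.** **Rules that stop lenalidomide.** Section 6.7 states: "Treatment with study drug is to be discontinued when any of the following occurs". The first listed event includes "effect/progressive disease as defined in section 8.0". Section 6.1 says that after cycle one "therapy with lenalidomide will continue in 28-day cycles, until there is disease progression, unacceptable toxicity or the patient chooses to withdraw from therapy". Neither section mentions the radiotherapy cohort.

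**Rules that continue it.** The Synopsis background says of patients who progress: "Patients will continue lenalidomide while undergoing local radiotherapy to a single site of disease", and then "Lenalidomide will then be continued until disease progression". The Synopsis study design says that "lenalidomide will be continued until disease progression or intolerance", with restaging every 2 months. The Synopsis dosing paragraph for the period after progression says: "Lenalidomide will be continued at the current dose, days 1-21 of a 28 day cycle". It also allows a stop after twelve cycles for a patient in complete response. Section 5.3 says: "Up to 10 patients who consent will continue lenalidomide and receive local radiotherapy to a single target lesion". Schedule footnotes 18 and 19 keep the most recent dose going throughout, and the cohort inclusion criteria in 5.4.1 require progression on protocol therapy.

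**How progression is measured.** Sections 8.5 and 8.6 count an SPD rise of at least 50% over nadir as progression. Sections 8.7 and 8.7.1 take the lowest measurement since the start of treatment as the reference. Section 8 has no cohort-specific baseline. Footnote 20 requires a scan that documents progression and then repeat imaging until complete response or progression, but it does not call that first scan a new reference.

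**The concern.** Two things do not fit together.

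First, the event that qualifies a patient for the cohort is the event at which 6.1 and 6.7 end the drug that the cohort continues. No section says which text prevails. Footnote 18 points to 5.3 and 6.5 for the cohort treatment. Section 5.3 carries the lenalidomide instruction, but 6.5 does not mention lenalidomide. Within section 6, the only progression rules for lenalidomide are therefore the two that stop it. A site must depart from one part of the protocol or the other, although section 13.2 in principle allows no deviations.

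Second, the cohort has its own stop at progression, and footnotes 20 to 22 show that a later, separate event was meant. That event is never defined apart from the one that admitted the patient. If the reference stays at the nadir on lenalidomide and rituximab, some patients already meet the definition on the day they enter. Progression recorded at the first cohort restaging would end lenalidomide and, under footnotes 20 and 21, the imaging and response assessment too. Stable disease would be misclassified, and a response that takes longer to appear could go unseen.

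**Working it through.** The plan gives no figure to reproduce here. The first part is a comparison of text; the second is simple arithmetic on the SPD rule.

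**Stop rule against cohort rule**

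| Question | 6.1 and 6.7 | Synopsis, 5.3, footnotes 18 and 19 |
|---|---|---|
| What happens to lenalidomide at progression? | It stops | It continues at the same dose, with local radiotherapy |
| Exception or precedence stated? | None | None |

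Read literally, the left column covers every cohort patient, because progression is the entry condition.

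**Progression reference: inputs**

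- Progression by SPD: at least 1.5 x nadir (8.5, 8.6).
- Reference: lowest value since treatment started (8.7, 8.7.1), with no reset at cohort entry.
- Partial response: SPD down by at least 50% (8.3).
- r = entry SPD / nadir SPD. For entry by the SPD rule, r is at least 1.5 by definition. The documents give no actual values, so anything above 1.5 is an assumption.
- The nodes that grew are not the one irradiated. The PET condition and the size floor for small nodes in 8.5 are taken as still met.

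**Step 1: unchanged disease.** Restaging SPD = r x nadir, which is at least 1.5 x nadir. Progression is met, with no assumption about the size of r.

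**Step 2: shrinkage by a fraction s from entry.** SPD = r(1 - s) x nadir. Progression is still met when r(1 - s) >= 1.5, that is, when s <= 1 - 1.5/r. Expressed as a multiple of entry SPD, the threshold without a reset is 1.5/r. With a reset, the threshold at first restaging is 1.5, before any fall below entry.

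| r | Largest shrinkage still called progression | Threshold without reset (x entry) | Restaging SPD (x entry) where the two rules disagree |
|---|---|---|---|
| 1.5 | 1 - 1.5/1.5 = 0% | 1.00 | 1.00 to 1.50 |
| 2 | 1 - 1.5/2 = 25% | 0.75 | 0.75 to 1.50 |
| 2.5 | 1 - 1.5/2.5 = 40% | 0.60 | 0.60 to 1.50 |

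Worked example with assumed values: nadir SPD 10 gives a threshold of 15. A patient who enters at 25 and shrinks by 30% to 17.5 is still above 15 and is called progressive. With a reset, the threshold would be 1.5 x 25 = 37.5 and the patient would be stable.

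**Step 3: can a response be called progression?** A 50% fall from entry leaves 0.5r x nadir. That reaches 1.5 x nadir only if r >= 3. For every r in the table, a patient with a 50% fall from entry clears the SPD rule, so the disagreement falls on stable disease.

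**Step 4: which new reference?** After a fall s from entry, nadir since entry puts progression at 1.5(1 - s) x entry: 1.125 for s = 25% and 0.75 for s = 50%. A fixed entry scan would wait until SPD reached 1.5/(1 - s) times the new nadir: 2.0 and 3.0 times. The nadir since entry is the better choice.

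**The case against.** The strongest reply is that the cohort rule is explicit, specific and repeated in the Synopsis, section 5.3 and the footnotes, and that the schedule has its own column for radiation after progression. A cohort defined by progression cannot be run if the drug stops at progression, so 6.1 and 6.7 are naturally read as the general rule for lenalidomide with rituximab. That stands. A reader might infer that the protocol leaves it open whether lenalidomide continues, or that the cohort design is unsound. The documents do not support either, and most sites would probably follow the intent.

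On the reference scan, one can argue that footnotes 20 to 22 already imply a fresh assessment, and that the start of treatment in 8.7 and 8.7.1 might mean the start of cohort treatment. The footnotes do show that a later event was intended. They do not say what it is measured from, and nadir in 8.5 and 8.6 carries no reset. Clear intent settles whether to continue the drug, but not which scan is the reference.

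A third point also stands: the effect on the cohort's non-target response objective is mostly indirect. A reader might infer that true responses would be recorded as progression. By Step 3, that needs r of 3 or more. The likelier loss is a response that would have come after lenalidomide and imaging had stopped.

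**Conclusion.** The point holds in two parts of unequal weight. The stop rules in 6.1 and 6.7 conflict with the cohort regimen as worded; this needs reconciling but is not a design flaw. The missing reset in section 8 is the more substantive part, because applying the stated definition gives a wrong classification: unchanged non-irradiated nodes count as progression at the first restaging for any patient who entered by the SPD rule on those nodes.

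The size is limited. The cohort is optional, has at most 10 of about 30 patients, and is exploratory under 11.3. The reset problem does not arise for patients who enter only by a new lesion, or whose only grown node is the one irradiated. The number affected is not given and cannot be derived. It would be wrong to infer that the whole cohort would be misclassified, or that the primary response analysis of lenalidomide with rituximab is affected. Even so, 11.3 treats any single response in the cohort as grounds for further study, so the handling of individual patients matters. The change should be made. The unchanged-disease result rests only on the SPD definition and the condition that the grown nodes are not irradiated; the 25% and 40% figures rest on assumed values of r.

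**What to change.** 1. In 6.1 and in the progressive-disease item of 6.7, add: *except for patients entering the post-progression radiotherapy cohort (5.3, 6.5)*. Add the same words to the radiation prohibition in 6.6.1.3 for consistency.
2. State in 6.7 when cohort patients stop lenalidomide: at further progression after cohort entry, at unacceptable toxicity or intolerance, or optionally after twelve cycles if in complete response. This matches the Synopsis.
3. In section 8, make the progression scan required by footnote 20 the cohort baseline. Measure response in non-irradiated lesions from that scan, and measure further progression from the smallest measurement at or after it.

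The cost is one exception phrase in three places, one sentence on stopping, and one or two on the baseline. No scan, visit or procedure is added.
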